### 8.7.3 Other Efficacy Endpoints

The change from baseline for the following parameters will be summarized by visit.

- Serum GAG measures
- Functional development: Bayley-III scores: cognitive, language and motor development, and social emotions and adaptive behavior
- Cardiac ventricular mass
- Pulmonary function: pulse oximetry
- Biochemical markers of bone turnover
- Motor functioning

For serum GAG excretion, the percentage change from baseline will also be displayed

The value of CGI will be summarized by visit

## 8.8 Safety Analyses

### 8.8.1 Adverse Events

The Medical Dictionary for Regulatory Activities (MedDRA) will be used to code all AEs to a system organ class (SOC) and a preferred term.

An AE (classified by preferred term) will be considered a treatment emergent adverse event (TEAE) if it occurred on or after the first dose and was not present prior to the first dose in this study, or it was present at the first dose but increased in severity during this study.

Subject incidence of TEAEs will be tabulated by SOC and preferred term. Serious adverse events (SAEs), treatment-related TEAEs and treatment-related SAEs will also be summarized.

Detailed listings for all AEs, SAEs, treatment related TEAEs, treatment related SAEs, AEs leading to the discontinuation of study drug or discontinuation of study, and death will also be generated. The severity will be based on Common Terminology Criteria for Adverse Events (CTCAE), Version 4.0. If an AE cannot be graded based on CTCAE, the investigator will assign a severity based on 1 = mild, 2 = moderate, 3 = severe, 4 = life threatening, and 5 = Death.

Patterns of Infusion Associated Reactions (IARs) will be specifically evaluated throughout the study (see details in [Appendix](#)). IARs will be characterized into 4 distinct types based on timing of onset relative to the infusion and specific clinical manifestations: anaphylactoid, anaphylaxis, urticarial (with or without angioedema), and immune complex. Safety reporting of individual AEs will be recorded in parallel. Detailed listings of IARs will be provided.

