## 11 APPENDICES

### Identification and Timing of IARs

Hypersensitivity reactions including anaphylaxis, the most severe form, and less severe allergic reactions are identified risks from ERT, including potentially ERT with UX003.

**IMPORTANT:** All adverse events occurring from the onset of the study treatment infusion, and within four hours following the end of the infusion, regardless of the investigator's assessment of whether or not the event was related to study drug administration will be considered an IAR.

It is expected that the IARs of greatest clinical importance will fall into the category of hypersensitivity reactions. Managing severe infusion related reactions requires early signs and symptoms to be recognized and well trained clinicians in the management of acute events.

Infusion associated reactions (IARs) may or may not occur in a recognized pattern of immune-mediated responses. The following table lists patterns of IARs that have been observed:

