## Patterns of IARs

Type	Time of onset	Cardiovascular Hypotension Tachycardia	Pulmonary Respiratory distress Hypoxemia	Skin Urticaria Raised, red, itchy rash	Mucosa Tongue Throat Angioedema	Abdomen Cramping/pain Episodic/ Bowel/bladder	Joint Pain/swelling	Fever/Chills?	Labs
Anaphylactoid	Early in infusion*	+( (Mild tachycardia, occasional low BP)	++ (Drop O 2 saturation)	+/-	+/-	++	-	++	↓C3, ↓C4, ↓CH50 +IgG
Anaphylaxis	Early in infusion*	+++	++	-	-	-	-	-	+IgE +Skin test
Urticular with or without angioedema	Early to later in infusion	-	+/-	+++ (Rash starts in body creases/folds, starts central to peripheral)	+/-	-	-	-	+ IgE or +IgG +Skin test
Immune Complex	Day of infusion, 2-3 days after infusion	-	-	+/- (Rash)	-	++	++	-	+Blood/protein in the urine +IgG

\*Tend to see after initial increase in infusion rate

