**KEY:**  
 + Sign often present  
 ++, +++ Sign present and likely significant  
 +/- Sign may or may not be present  
 - Sign not typically present

**Anaphylactoid reactions** are the most important severe type of IAR and are caused by synchronous complement activation due to IgG1 antibodies to the enzyme and most commonly begins during the first hour after the infusion rate is increased. In MPS 7 mice, these types of reactions were observed approximately 4-6 weeks after infusions were started. The slow rate of infusion for one hour followed by the increased rate of infusion is expected to reduce clinical complement-mediated hypersensitivity responses, based on studies with laronidase in MPS 1 (Kakkis et al. 2001).

**True anaphylaxis** due to an IgE mediated response has not been observed as frequently, but still can occur at any time, though it would be expected to be early during the infusion. The premedication with an anti-histamine is primarily to minimize IgE mediated histamine release and to help mitigate a reaction if one were to occur.

**Urticular skin reactions** with or without angioedema (tongue and throat swelling) is a common type of reaction observed often after several months of therapy. This can be associated with substantial pruritis and discomfort. Increased premedication and slower infusion rates can help. With time, these type of reactions will tend to subside over a period

of weeks to months with continued therapy. Airway obstruction is potentially serious in patients with MPS who have enlarged tongues, tonsils and adenoids and floppy tracheal cartilage, so the appearance of angioedema requires particular care and caution in management.

**Immune complex disease** can be observed with ERT but is more difficult to discern and diagnose primarily because of the delay in onset and variable symptoms. Abdominal pain, joint pain/swelling, proteinuria/hematuria, and skin rashes within the 1-5 days after an infusion may indicate that the antigen-antibody ratio is close to 1:1 leading to polymerization of antigen- antibody complexes, which may precipitate and locally activate complement and result in tissue injury.

IARs may present as described above, or may present with variable signs and symptoms alone or in combination. This guide is intended to help investigators evaluate and treat subjects who experience an IAR with UX003 ERT.

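### The SAP's four-hour definition of an infusion-associated reaction omits all but early cases of one of its own four reaction types, and events that fit no type have no category

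*SAP*

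**What the plan says.** SAP 8.8.1 gives the typing rule: "IARs will be characterized into 4 distinct types based on timing of onset relative to the infusion and specific clinical manifestations". The types are anaphylactoid, anaphylaxis, urticarial (with or without angioedema) and immune complex. It points to the Appendix for details and names one dedicated output: "Detailed listings of IARs will be provided". Individual adverse events are recorded in parallel.

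The Appendix (SAP Section 11, Identification and Timing of IARs) defines the events. It takes in all adverse events "occurring from the onset of the study treatment infusion, and within four hours following the end of the infusion". The investigator's view of causality does not matter: "whether or not the event was related to study drug administration will be considered an IAR". It then says that IARs "may or may not occur in a recognized pattern of immune-mediated responses", and its closing paragraph adds that signs can vary and can occur singly or together.

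The Patterns of IARs table gives the immune complex onset as "Day of infusion, 2-3 days after infusion". The text below the table says 1 to 5 days after an infusion.

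**The concern.** The typing rule and the event definition come from the same document but cover different sets of events. One type is described mainly as a delayed reaction, while the definition closes four hours after the infusion ends. The definition also takes in events that need have nothing to do with hypersensitivity, while all four types are hypersensitivity patterns.

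Safety and tolerability form part of the primary objective. Protocol 5.4 treats IARs as the leading safety concern for enzyme replacement therapy, and SAP 3.4 states that no independent data monitoring committee is used. The IAR listing is where a reader will look for this risk. It should contain all four patterns that the SAP says it will evaluate, and two people preparing it should arrive at the same content.

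**Working it through.** The plan gives no figure to reproduce. The check sets the definition beside the types.

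**Direction 1: are all four types inside the definition?** The window ends 4 hours after the end of the infusion (Appendix). Converting days to elapsed hours:

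| Source of immune complex onset | Onset | Inside the window? |
|---|---|---|
| Table, first part | day of infusion | only if onset is no later than 4 h after the infusion ends |
| Table, second part | 2-3 days = 48-72 h | no, 48 > 4 |
| Text below the table | 1-5 days = 24-120 h | no, 24 > 4 |

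Counting the days from the start of an infusion lasting about 4 hours (Protocol 7.4) changes nothing: 24 - 4 = 20 h after its end, still more than 4. So only the early part of the day-of-infusion range qualifies. The table and the text also give different delayed ranges (2-3 and 1-5 days), so the Appendix offers no single alternative window to use instead.

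**Direction 2: do the types cover everything the definition admits?** The definition requires timing only. An unrelated viral fever or a fall during an infusion is an IAR. The rule offers four hypersensitivity types and no other, mixed or unclassified type. The Appendix acknowledges events without a recognized pattern and events with combined signs, but neither it nor 8.8.1 says how to record their type or who assigns it.

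**What happens to the affected events?**

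- Protocol 7.5.4.9 collects adverse events from consent until 30 days after the last dose, so delayed reactions are recorded.
- SAP 8.8.1 tabulates treatment-emergent events by system organ class and preferred term, summarizes serious events, and lists all adverse events.
- No table or test by IAR type is specified.

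No event is lost from the safety data. What is lost is the link between a delayed event, the preceding infusion and the immune complex pattern in the IAR listing. For events that fit no pattern, what is missing is a defined entry for type.

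**The case against.** *The definition says what is an IAR, not what is excluded.* The Appendix sentence is inclusive, and the table beneath it presents delayed immune complex disease as an IAR pattern. A medical reviewer might well include such cases. That is probably the intention, but the four-hour window is the only selection rule given. Anyone building the listing from it would leave delayed cases out, and anyone wishing to include them must choose between two onset ranges.

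*The rule does not say that every IAR must be typed.* This stands. A reader might infer that an unrelated event is forced into a hypersensitivity label. That is only one reading: 8.8.1 says neither each nor every, and the Appendix lets an IAR follow no pattern, so such an event could be left untyped. What remains is that the SAP does not say which.

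*The table separates anaphylaxis from anaphylactoid reactions.* A reader might infer that this boundary is undefined and that anaphylaxis would be under-counted. Both rows do share an early onset and the same pulmonary mark, and their circulatory marks differ in degree ("Mild tachycardia, occasional low BP" in the anaphylactoid row against the strongest mark for anaphylaxis). However, the abdominal and fever/chills columns differ (++ against -), the laboratory column differs, and the text describes the timing somewhat differently. Because - means only "Sign not typically present", the boundary is soft, but it is not undefined. Nothing in the documents shows an under-count.

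*No planned result depends on the label.* This stands and sets the severity. With about 15 children, each case can be read individually.

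**Conclusion.** The SAP is wrong as written on a minor point. If the four-hour window is taken as the complete IAR definition, the evaluation and listing leave out immune complex reactions except those starting early on the day of infusion, although immune complex is one of the four types to be characterized. Separately, unrelated and mixed events that qualify as IARs have no category.

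The first conclusion rests on reading the Appendix sentence as the selection rule for the listing and the onset times as elapsed time. Its practical size cannot be stated. The documents give neither a frequency for immune complex reactions nor a background adverse event rate, and the number of infusions actually given depends on how many children complete. A reader might want a count of chance events falling in the window, but any such figure would come from an assumed rate. If no delayed reaction occurs, the first gap has no effect. In any case, the adverse event and serious adverse event tables and listings are unaffected.

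**What to change.** In SAP 8.8.1 and the Appendix:

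1. State that immune complex reactions are sought among adverse events with onset up to 5 days after an infusion, that they are listed with the IARs, and that those beyond the four-hour window are flagged as delayed.
2. Restrict this extended search to the signs the Appendix names: abdominal pain, joint pain or swelling, proteinuria or hematuria, and rash.
3. Use one onset range in both the table and the text.
4. Add a mixed/unclassified type, so that one of the four patterns is assigned only when an event fits it, and say who assigns the type.

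The cost is a few sentences and one derived flag, using adverse events already recorded and MedDRA-coded. The downside is background noise. With infusions every 14 days, a 5-day window covers 5/14 = 36% of treatment time, so an unrestricted search would pick up many unrelated events. Item 2 limits this, and the delayed flag keeps these events apart from those in the four-hour window.

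A MedDRA standardised query for anaphylactic reaction, with medical review of each case, would be a reasonable optional addition, but the documents do not show that it is needed.

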### 8.8.2 Laboratory Parameters

Clinical laboratory values (in SI units) and changes from baseline at each assessment time point will be summarized for clinical laboratory parameters in hematology, chemistry, urinalysis and thyroids panels. Abnormal values will be flagged. The frequency and percentage of subjects who experience abnormal clinical laboratory results (i.e. outside of reference ranges) and/or clinically significant abnormalities after study drug administration will be presented by clinical laboratory measurement.

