#### 7.5.4.5 Clinical Laboratory Tests for Safety

The clinical laboratory evaluations to be performed in this study are listed in Table 7.5.4.5.1. Clinical laboratory testing for serum chemistry, hematology, and urinalysis will be performed at the Screening, Baseline (Week 0), Week 2, 4, and 8 visits. After Week 8, clinical laboratory evaluations will be performed every 8 weeks until Week 48 (or Early Termination visit). During the Continuation Period, clinical laboratory testing will be performed at 24-week intervals as indicated in the Schedule of Events (Table 2.1). Blood and urine samples will be collected prior to administration of study drug; fasting is not required. See Section 7.4.3.1 for infusion related fasting and refer to the Laboratory Manual for additional details.

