#### **7.5.4.9 Adverse Events**

All AEs will be recorded from the time the subject signs the informed consent until 30 days after the last dose of study drug. The determination, evaluation, reporting, and follow-up of AEs will be performed as outlined in Section 8.5. At each visit subjects will be asked about any new or ongoing AEs since the previous visit. Assessments of AEs will occur at each study visit.

Clinically significant changes from study baseline in physical examination findings, weight, vital signs, and clinical laboratory parameters, will be recorded as AEs or SAEs, if appropriate.

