### **7.6.7 Safety Analyses**

The primary safety analysis will evaluate the safety of UX003 as measured by the incidence, frequency and severity of AEs and SAEs, including clinically significant changes from study baseline to scheduled time points in:

- Vital signs and weight
- Physical examination findings
- Clinical laboratory evaluations

- Concomitant medications
- IgG antibodies to rhGUS
- Complement C3, C4 and CH50 levels (as indicated)

All AEs will be coded using the Medical Dictionary for Regulatory Activities (MedDRA). The incidence and frequency of AEs will be summarized by System Organ Class (SOC), Preferred Term (PT), relationship to study drug, and severity. No statistical significance will be assessed. A by-subject listing will be provided for those subjects who experience a SAE, including death, or experience an AE associated with early withdrawal from the study or study drug treatment.

Clinical laboratory data will be summarized by the type of laboratory test. The frequency and percentage of subjects who experience abnormal clinical laboratory results (i.e. outside of reference ranges) and/or clinically significant abnormalities after study drug administration will be presented for each clinical laboratory measurement. For each clinical laboratory measurement, descriptive statistics will be provided for study baseline and all subsequent visits. Changes from study baseline to the post-treatment visits will also be provided. Descriptive statistics of vital signs, imaging assessments for safety, and concomitant medications will be provided in a similar manner.

Changes in findings from study baseline physical examinations will be tabulated and listed for each subject by examination category. If there are examination findings that change in more than one subject, these will be tabulated in a separate table and expressed as the number of subjects with the change out of the total.

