**Table 7.3–1. Visit Time Windows**

Period	Visit	Scheduled Visit Day	Window
48-Week Treatment Period	Baseline	Day 1	Days $\leq 1$
	Week 12	Day 85	Days [2, 127]
	Week 24	Day 169	Days [128, 211]
	Week 36	Day 253	Days [212, 295]
	Week 48	Day 337	For subjects entered into continuation period Days [296, start of continuation period-1] For subjects did not enter into continuation period Days $\geq 296$
Continuation Period Weeks 50-240	Week 60	Day 421	Days [start of continuation period, 463]
	Every 12 Weeks	Day $84x^a+421$	[380+84x, 463+84x]
	Week 240	Day 1681	Days $\geq 1640$

a x=1,2...14

End of Treatment visit for subjects who didn't complete either the 48-week treatment period or the continuation period, and unscheduled visits will be mapped to the closest post baseline scheduled visits if the scheduled visits are missing. If there are more than one unscheduled/end of study visits mapped to the same window, the one closer to the target day will be used. If more than one visits have the equal distance to the target day then the later one will be used, if more than one visits on the same day, use the time or the sequence number to select the later record. For listings and shift tables, all data points will be included.

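### The laboratory abnormality count in SAP 8.8.2 has no baseline condition, so one descriptive safety table mixes pre-existing, chance and new abnormalities

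*SAP*

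**What the plan says.** For each laboratory measurement, SAP 8.8.2 gives the number and percentage of "subjects who experience abnormal clinical laboratory results (i.e. outside of reference ranges) and/or clinically significant abnormalities after study drug administration". Protocol 7.6.7 and the synopsis carry the same rule: "abnormal clinical laboratory results (i.e. outside of reference ranges) and/or clinically significant abnormalities after study drug administration will be presented for each clinical laboratory measurement". None of them asks for an in-range value before dosing, a worsening, a toxicity grade or a repeat.

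The adverse event rule in SAP 8.8.1 does look back. An event is treatment-emergent if "it occurred on or after the first dose and was not present prior to the first dose in this study", or if it was there at the first dose and then became more severe.

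The plan handles baseline laboratory values in other ways:
- SAP 8.8.2 itself says that values and "changes from baseline at each assessment time point will be summarized for clinical laboratory parameters", and that abnormal values are flagged.
- SAP 8.1 puts all raw and derived data into listings or graphs because the sample is small.
- Protocol 7.5.4.9 says: "Clinically significant changes from study baseline in physical examination findings, weight, vital signs, and clinical laboratory parameters, will be recorded as AEs or SAEs", where appropriate.
- SAP 7.3 adds a data rule, "For listings and shift tables, all data points will be included", but no section of the SAP specifies a laboratory shift table.

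**The concern.** Safety is part of the primary objective, there is one treatment group, and the children enter with multi-organ disease; about 5 of about 15 are planned to have hydrops fetalis. A child whose result was out of range before the first dose, and stays there, is counted in a table described as showing abnormalities after study drug. So is a child with one stray value among repeated panels. With no control arm there is no background rate to set against the percentage. A reader of that table cannot tell pre-existing, chance and new abnormalities apart. The and/or wording adds a second ambiguity: a trivial excursion and a clinically significant result fall into the same numerator.

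**Working it through.** The documents state no expected figure for this count, so there is none to reproduce. The check asks how often the rule as written flags a child when the drug does nothing.

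**Inputs from the documents.** Protocol 7.5.4.5 says that testing "will be performed at the Screening, Baseline (Week 0), Week 2, 4, and 8 visits", then every 8 weeks to Week 48. The scheduled post-dose panels are Weeks 2, 4, 8, 16, 24, 32, 40 and 48, so k = 8. Testing every 24 weeks in the Continuation Period adds Weeks 72 to 240, another 8, so k = 16. The planned number of children is about 15.

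**Assumptions, not in the documents.** A reference range covers 95% of healthy values (p = 0.05 per test), all panels are attended, and there is no drug effect. Within-child correlation ρ is varied. This describes quantitative analytes only; urinalysis items such as appearance, color and nitrite in Protocol Table 7.5.4.5.1 are qualitative.

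**Independent tests.** P(flagged) = 1 − (1 − p)^k.
- To Week 48: 1 − 0.95^8 = 33.7%; 15 × 0.337 = 5.05 children.
- To Week 240: 1 − 0.95^16 = 56.0%; 15 × 0.560 = 8.4 children.
- With p = 0.025 (one-sided limits): 18.3% and 33.3%.

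**Correlated tests.** Simulate one baseline and 8 post-dose standard normal values per child with common correlation ρ (400,000 draws). A value is out of range beyond ±1.96. Results for a child with healthy values, to Week 48:

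| ρ | Flagged as written | Expected of 15 | In range at baseline, then out (of all) | Same, of children at risk | Same, with two consecutive panels out (of all) |
|---|---|---|---|---|---|
| 0 | 33.7% | 5.05 | 32.0% | 33.7% | 1.6% |
| 0.5 | 25.0% | 3.8 | 21.9% | 23.1% | 2.9% |
| 0.7 | 19.1% | 2.9 | 15.3% | 16.1% | 3.1% |
| 0.9 | 11.8% | 1.8 | 7.3% | 7.7% | 2.2% |

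At ρ = 0.7 the at-risk figure is 0.153 / 0.95 = 16.1%. The baseline condition therefore removes (19.1 − 15.3) / 19.1 = 20% of the chance flags there, with a range of 5% (ρ = 0) to 38% (ρ = 0.9). Asking for two consecutive out-of-range panels as well removes most of the rest.

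**Pre-existing disease.** The documents give no baseline rate of abnormal results, so it is varied by shifting the mean 0, 1.0, 1.96 or 3.0 SD. At ρ = 0.7, with no drug effect:

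| Out of range at baseline (assumed) | Flagged by Week 48 as written | Share of those flagged already abnormal at baseline |
|---|---|---|
| 5% | 19.1% | 20% |
| 17% | 42.9% | 36% |
| 50% | 80.7% | 60% |
| 85% | 97.9% | 87% |

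The last column runs from 20% to 87%, so the documents cannot fix it. Where half are abnormal at baseline, 63.7% of the children at risk would still be flagged after the baseline condition, because many of them sit close to the limit.

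**The case against.** The strongest reply is that the plan already handles baseline laboratory values and that this table decides nothing. Much of that stands. The same section summarizes changes from baseline at every time point. With about 15 children, flagged listings of all data let a reader follow each child. Clinically significant laboratory changes from baseline go to adverse event reporting and so meet the treatment-emergent rule. No significance is assessed for safety, and no alpha, sample size or decision rule uses the count.

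These points limit the harm but do not correct the percentage. By-visit summaries can hide one child's new abnormality, the adverse event route depends on the investigator's judgment, and listings leave the reader to rebuild the answer. The shift tables in SAP 7.3 are mentioned in a visit-selection rule and tied to no parameter.

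Three stronger readings are tempting and are not supported:
- That the laboratory plan ignores baseline, or that this count is its main summary. SAP 8.8.2 names values and changes from baseline first and does not rank the count above them.
- That the count mostly measures baseline disease and number of tests. That needs a baseline abnormality rate that the documents do not give.
- That a real new abnormality would be lost. The listings and the adverse event route would still show it.

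It is also fair to object that a baseline condition alone does not cure chance flags. The calculation confirms this, and the fix allows for it.

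**Conclusion.** The point holds for one table. As defined, the count cannot separate abnormalities that were there before dosing, those that arise by chance over repeated panels, and new ones, and it merges two kinds of result. With no drug effect and 95% reference ranges, a healthy child is flagged per quantitative analyte with probability 19% (ρ = 0.7) to 34% (independent tests) by Week 48, or about 3 to 5 of 15 children; at ρ = 0.9 it is 12%. The reference range coverage and the correlations are assumptions. The part due to pre-existing disease is unknown. The consequence is for the interpretation of a descriptive single-arm safety summary. The change is worth making because it is cheap and brings the laboratory count into line with the rule already used for adverse events.

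**What to change.** In SAP 8.8.2:
1. Report new or worsened abnormalities: in range at baseline and out of range afterwards, or a worse CTCAE grade than at baseline. Use the baseline of SAP 5.1 and state the denominator, namely the children at risk at baseline for that analyte. For a child treated earlier under an emergency IND this baseline is not untreated, so footnote it.
2. Report out-of-range and clinically significant results as two separate counts.
3. Specify a laboratory shift table from baseline to worst post-dose value (low, normal, high, or CTCAE grade where the scale covers the analyte).
4. State that the baseline condition removes pre-existing abnormality but only a minor part of chance flags. Therefore also show abnormalities that reach a CTCAE grade or persist at the next scheduled panel, and mark those first seen at a child's last panel as not confirmable.

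The cost is SAP wording and programming. Screening and Week 0 samples are already taken and CTCAE is already the adverse event scale, so no new data are needed. The downside is one or two more tables.
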